¹⁵If RCL screening tests are negative up to and including the Month 12 Visit, RCL screening will cease, and the Month 24 co-culture RCL sample only will be collected and archived.

¹⁶CBC with differential and VCN are to be carried out whenever ISA is performed.

¹⁷In exceptional situations NGS mutational testing may be performed by a local lab upon agreement with the Medical Monitor.

¹⁸See [Section 6.2.21](#).

¹⁹Post drug product infusion, bone marrow aspirate is to be taken per SOE unless discussed with the Medical Monitor for exceptions, such as if not clinically appropriate per local standard of care (e.g., bone marrow aspirate would require general anesthesia which would be considered an unacceptable risk to the subject) or not considered by the Investigator to be in the best interest of the subject to perform.

²⁰Bone marrow smear should be read locally; additional bone marrow slides are to be archived for potential central analyses.

²¹Conventional cytogenetics should be performed locally

²²See [Section 6.2.21](#).

²³Cerebral MRA/MRI alternative procedure: For subjects unable to undergo cerebral MRA/MRI, a CT scan can be performed instead.

²⁴For subjects who have a medical history of iron overload or serum ferritin > 1000 ng/mL, a cardiac MRI is required at Screening and at Month 24 Visit.

²⁵Including % predicted FVC, % predicted FEV1; % predicted RV; and % predicted DLCO (corrected for Hb). Adapt to pediatric use per institutional practices.

²⁶Subjects should complete PRO questionnaires at the beginning of the Visit (prior to undergoing any other procedures during the Visit).

²⁷If the Month 18 Visit does not include 18 calendar months, a telephone contact assessment for VOEs is to take place after 18 calendar months (post-drug product infusion) have elapsed.

.

6.2. Study Measures

6.2.1. Demographics and Medical History

Subject demographic data such as gender, age, race, and ethnicity, will be obtained at Screening, as per the SOE.

Medical history is to include all prior and current medical history, e.g., history of infectious events (including aplastic crises), iron overload, thromboembolism events, surgical procedures, medications (including pain medications).

6.2.2. SCD-specific History and Outcome Measures

Sickle cell disease-specific medical history will be obtained at Screening as per the SOE, including the following:

1. Any history of severe cerebral vasculopathy event, stroke, or TCD acceleration and any associated visits to medical facilities and/or hospitals prior to Informed Consent.
History of any other acute or chronic SCD-related complications and any associated visits to medical facilities and/or hospitals in the 24 months prior to Informed Consent. Sickle cell disease-related complications may include, but are not limited to, any of the following:
 - VOEs/severe VOEs, pulmonary hypertension (TRJV), cardiomyopathy, osteonecrosis, gall bladder lithiasis, leg (skin) ulceration, sickle cell nephropathy, silent cerebral infarct, transient ischemic attack
2. Baseline Hb, as defined in [Section 7.4.1](#)
3. History of HU use, including any history of HU intolerance or failure.
4. History of L-glutamine use
5. History of pRBC transfusions (including date, indications, mL/kg and units of pRBCs, associated pre-transfusion HbS and total Hb values and post-transfusion AEs [including allo-immunization]) within the 24 months prior to Informed Consent will be obtained at Screening, as per the SOE. Iron chelator use within the 24 months prior to Informed Consent
6. In addition, for subjects who are receiving regular transfusions at the time of study entry:
 - other indication for chronic transfusions
 - if available, the history of VOEs/severe VOEs for the 2 years prior to the date at which regular transfusions started should be documented.

6.2.3. Physical Examination and Performance Status

A complete physical examination is to be conducted as per the SOE for the identification of medical history or AEs and reported on the appropriate CRF.

Screening PE and performance status should be performed within 90 days prior to mobilization. If > 90 days has elapsed, PE and performance status should be re-assessed during the screening period.

Any leg (skin) ulceration noted upon physical exam or as part of medical history must include severity classification.

Karnofsky and Lansky performance status (see [Appendix 10.1](#)) is to be assessed as per the SOE.

Additionally, Tanner staging (subjects < 18 years of age) should be performed at Screening and every 6 months after infusion during puberty.

6.2.4. Vital Signs

Vital signs are to be measured per the SOE and include systolic/diastolic blood pressure, pulse, temperature, oxygen saturation, weight, height, and pain evaluation. Screening vital signs should be performed within 90 days prior to mobilization. If > 90 days has elapsed, vital signs should be re-assessed during the screening period.

6.2.5. Vaso-occlusive Events (VOEs)

All VOEs 24 months prior to ICF and following ICF for the duration of the study will be recorded. VOE categories include acute pain with no medically determined cause other than VOE (e.g., VOC), acute chest syndrome (ACS), acute hepatic sequestration, acute splenic sequestration, and acute priapism. All VOEs that, in the opinion of the Investigator, represent at least one of these events (regardless of duration, severity, treatment, or need for medical facility visit) must be recorded. A VOE can be home-managed only, and does not require a visit to a medical facility or hospitalization to be reported. It is recognized that retrospective collection of VOE information may be challenging; however, complete collection and reporting of VOEs should be done to the best of the clinical site's ability.

Subject eligibility is determined by the Investigator based on that subject having at least 4 protocol-defined severe VOEs (i.e., protocol sVOEs) in the 24 months prior to ICF as set forth in [Section 4.2](#).

For the purposes of this study, a protocol-defined VOE (i.e., protocol VOE) is any of the following events (with or without hospitalization):

- a. an episode of acute pain with no medically determined cause other than a VOE (e.g., VOC) lasting more than 2 hours and requiring care at a medical facility
- b. ACS, defined by an acute event with pneumonia-like symptoms (e.g., chest pain, fever [$> 38.5^{\circ}\text{C}$], tachypnea, wheezing or cough, or findings upon lung auscultation), and the presence of a new pulmonary infiltrate consistent with ACS, and requiring oxygen treatment and/or blood transfusion
- c. acute hepatic sequestration, defined by a sudden increase in liver size associated with pain in the right upper quadrant, abnormal results of liver-function test not due to biliary tract disease, and reduction in Hb concentration by at least 2 g/dL below the baseline value
- d. acute splenic sequestration, defined as sudden enlargement of the spleen and reduction in Hb concentration by at least 2 g/dL below the baseline value

- e. an event of acute priapism: defined as a sustained, unwanted painful erection lasting more than 2 hours and requiring care at a medical facility

A protocol sVOE is defined for the purposes of this study as a protocol VOE requiring \geq 24-hour hospital or emergency room (ER) observation unit visit, or at least 2 visits to a day unit or ER over 72 hours with both visits requiring intravenous treatment, with the exception of priapism (all protocol VOEs of priapism are also protocol sVOEs).

All reported VOEs will also be adjudicated by an independent event adjudication committee for purposes of endpoint analysis (see [Section 3.3](#)).

6.2.6. Pain Assessment

Acute pain will be assessed as part of the patient-reported outcome assessment by PROMIS (see [Section 6.2.26](#)).

Chronic pain will be assessed per the SOE and includes evaluation of the following AAPT Diagnostic Criteria for Chronic Pain Associated with SCD [adapted from ([Dampier et al. 2017](#))]:

1. Reports of ongoing pain present on most days over the past 6 months either in a single location or in multiple locations
2. Must display at least 1 sign:
 - Palpation of the region of reported pain elicits focal pain or tenderness
 - Movement of the region of reported pain elicits focal pain
 - Decreased range of motion or weakness in the region of reported pain
 - Evidence of skin ulcer in the region of reported pain
 - Evidence of hepatobiliary or splenic imaging abnormalities (e.g., splenic infarct, chronic pancreatitis) consistent with the region of reported pain
 - Evidence of imaging abnormalities consistent with bone infarction or avascular necrosis in the region of reported pain
3. There is no other diagnosis that better explains the signs and symptoms

6.2.7. Clinical Laboratory Tests

Blood samples for clinical laboratory tests, including hematology, serum chemistry, liver function tests, renal function tests, coagulation studies, and iron studies, are to be collected per the SOE. These tests are to be performed by the local laboratory and reviewed by the Investigator or qualified designee (e.g., physician's assistant, nurse practitioner).

Screening clinical labs should be performed within 90 days prior to mobilization. If $>$ 90 days has elapsed, clinical labs should be re-assessed during the screening period.

The following clinical laboratory parameters are to be determined:

Hematology	Serum chemistry	Liver function tests	Coagulation
complete blood count [CBC] with differential, reticulocyte count, nucleated erythrocytes, platelets, haptoglobin	sodium potassium chloride bicarbonate creatinine albumin glucose CRP blood urea nitrogen calcium uric acid phosphate total protein magnesium lactate dehydrogenase erythropoietin estimated glomerular filtration rate (as determined using the Chronic Kidney Disease Epidemiology Collaboration (CKD-EPI) equation)	aspartate aminotransferase alanine aminotransferase alkaline phosphatase total and direct bilirubin gamma-glutamyl transferase	prothrombin time [PT]/activated partial thromboplastin time [aPTT] D-Dimers
Iron studies			

Urine for urinalysis (sent to local lab) is to be collected per the SOE, and urinalysis includes color, appearance, specific gravity, pH, microalbumin, protein, creatinine, glucose, ketones, occult blood.

Additional clinical laboratory tests may be performed at the Investigator's discretion.

6.2.7.1. Clinical Work-up for Unexpected Blood Test Results

If the results from blood tests are not as expected, additional testing may need to be performed to allow for further investigation and may include:

- Physical exam
- Blood tests
- Imaging tests
- Bone marrow biopsy and/or aspiration (may also be archived for additional analysis in the future; see [Section 6.2.21](#))

6.2.8. Additional Laboratory Tests

Blood samples will be collected for additional eligibility-determining laboratory tests, according to the SOEs.

- **Serology**

Screening serology will be evaluated using standard methods. The serology panel for eligibility includes HIV-1 and HIV-2; hepatitis B core antibody (HBcAb); hepatitis B surface antibody (HBsAb); hepatitis B surface antigen (HBsAg); hepatitis C virus (HCV) antibody; varicella zoster virus (VZV) IgG; HTLV-1 and HTLV-2, syphilis (RPR), toxoplasmosis, Trypanosoma cruzi, and West Nile Virus. Any other serology required by institutional guidelines before stem cell harvest and transplantation of drug product (including, for example, testing for CMV, EBV, and HSV) are permitted.

For subjects with exposure risks for HIV, HBV and HCV, these assessments should also be repeated during the preconditioning visit. Where clinically and/or regionally indicated, other tests for infectious pathogens may be performed, as required by regional regulations or at physician discretion.

- **Serum β -human chorionic gonadotropin pregnancy test**

Only required for females of child-bearing potential.

6.2.9. Hormonal Testing

Hormonal testing is to be performed as per the SOE and includes: estradiol, (females only); total testosterone (males only); TSH, free T3, free T4, AM cortisol, ACTH, 25 OH Vitamin D, PTH, FSH, LH (all subjects).

Hormonal testing should be performed within 90 days prior to mobilization. If > 90 days has elapsed, PE and performance status should be re-assessed during the screening period.

6.2.10. Sperm / Testicular Tissue or Oocyte Banking

Sperm or testicular tissue banking for males or oocyte aspiration following ovarian stimulation and cryopreservation for females will be done at the discretion of the subject. If a subject elects to undergo these procedures, the procedures must occur during the period between mobilization and conditioning and can be done at any time before the start of conditioning once enough cells have been harvested for drug product manufacture. If surgery is required, this must be done a minimum of 2 weeks prior to initiation of conditioning. Subjects must be transfused within 4 days prior to surgery.

6.2.11. Reconfirmation of Suitability for Transplant

At Pre-conditioning, review CBC, serum chemistry (chemistry will include sodium, potassium, chloride, bicarbonate, blood urea nitrogen, creatinine, calcium, magnesium, phosphate, albumin, total protein, uric acid, LDH, liver enzymes (GGT, ALP, ALT, AST, direct and total bilirubin), glucose and CRP), physical examination, cytogenetics, and performance status; verification that the drug product has been dispositioned for clinical use, is available on site and that back-up cells are available. If PFTs have not been performed within 3 months of initiation of conditioning, then these tests must be repeated prior to conditioning. While not mandatory, cardiac Doppler echocardiology (including LVEF) and cerebral MRI should be repeated prior to conditioning if clinically indicated.

Bone marrow aspirate will be collected prior to conditioning for assessment of chromosomal abnormalities or genetic mutations, particularly those associated with myelodysplastic syndrome (MDS) or acute myeloid leukemia (AML), by conventional cytogenetics (karyotyping). These results will be used to assess individual benefit-risk for a subject's suitability to proceed with HSCT. If a chromosomal abnormality that may put the subject at an increased risk of MDS/AML per the Investigator's judgment is identified in the bone marrow prior to conditioning, the subject will be withdrawn from the study and not proceed with conditioning or treatment with bb1111. If other chromosomal abnormalities are identified in the bone marrow prior to conditioning that do not render the subject ineligible for HSCT per the Investigator's judgment, approval of the Medical Monitor is required before the subject can proceed with conditioning, and the subject can proceed with conditioning and treatment with bb1111 after providing appropriate informed consent.

6.2.12. Immunological studies

Immunological testing includes measuring levels of T cells (CD3), T cell subsets (CD4, CD8), B cells (CD19), and natural killer cells (CD16/CD56), irregular antibodies, and antibody titers against tetanus, pneumococcus, and measles/mumps/rubella.

Screening for irregular antibodies is required for all subjects at Screening. Screening for new irregular antibodies is required at Month 2 and Month 3 and may also occur at physician's discretion. For subjects who receive their final pRBC transfusion after the Month 3 Visit, screening for new irregular antibodies must be performed at the scheduled visit occurring immediately after last pRBC transfusion.

6.2.13. Brain Natriuretic Peptide

Blood samples are to be collected per the SOE for BNP. This assay should be performed at the local laboratory.

6.2.14. Busulfan concentrations

Blood for measuring busulfan PK and making appropriate adjustments of the busulfan dose should be drawn for local testing as per [Section 5.2.5.2](#).

6.2.15. Hemoglobin Analysis

Blood samples are to be collected per the SOE for assessment at a central laboratory of globin chain levels by HPLC, including β^{A-T87Q} -globin. Blood sample collection details are included in the Laboratory Manual for this study.

Blood samples will also be collected per the SOE to assay for methemoglobin concentration (specialty lab).

Additionally, blood samples will be analyzed by electrophoresis in local laboratories to monitor the percentages of HbS and HbA during the transfusion regimen through hospital discharge post-infusion (HbF results should be collected if available).

6.2.16. Testing for SCD Genotype, Vector Copy Number, Replication Competent Lentivirus, and Integration Site Analysis

Blood samples will be collected according to the SOE for assessments of the following:

- SCD genotype
- VCN
- RCL
- Integration site analysis (ISA)

Blood sample collection details are included in the Laboratory Manual for this study.

Note that ISA may be discontinued if a subject's VCN is less than 0.01 copies per cell.

Results from these analyses may be accessed by viewing the appropriate electronic case report forms within the electronic data capture system.

6.2.17. Bone Marrow Aspiration

Bone marrow aspirate is to be taken per SOE. After drug product infusion, a bone marrow aspirate is to be taken unless discussed with the Medical Monitor for exceptions, such as if not clinically appropriate per local standard of care (e.g., bone marrow aspirate would require general anesthesia which would be considered an unacceptable risk to the subject) or not considered by the Investigator to be in the best interest of the subject to perform. A bone marrow smear is to be collected at the time of each bone marrow aspiration; site monitoring to include: cell count and differential, cellularity, M:E ratio, peripheral smear, iron stores, and morphologic report at a minimum (refer to SOM for additional detail). The bone marrow aspiration will be performed in accordance with institutional practices. Bone marrow smears should be read locally; additional bone marrow slides are to be archived for potential central analyses. Bone marrow aspirate collection details are included in the Laboratory Manual.

Bone marrow samples will be used for cytogenetics and mutational testing ([Section 6.2.18](#)), and storage (including slides; see [Section 6.2.21](#)), and may also be used for CCI [REDACTED] PD ([Section 6.2.19](#)).

6.2.18. Conventional Cytogenetics (Karyotyping) and NGS Mutational Testing

Bone marrow aspirate (see [Section 6.2.17](#)) and blood will be collected according to the SOE for assessment of chromosomal abnormalities or genetic mutations, particularly those associated with myelodysplastic syndrome (MDS) or acute myeloid leukemia (AML), by conventional cytogenetics (karyotyping) and NGS mutational testing.

If available, bone marrow and blood samples collected per SOE may be used for retrospective genetic testing.

Results from conventional cytogenetics (karyotyping) from the bone marrow prior to conditioning will be used to assess suitability for transplant (see [Section 6.2.11](#)).

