Subjects in Group B2 who tolerated and effectively mobilized with plerixafor were given the option to postpone drug product manufacture until Group C opened, to allow drug product manufacture using plerixafor mobilized cells. In Group C, subjects for whom adequate HSCs are collected to achieve the minimum cell dose but not for rescue, and who do not tolerate plerixafor or do not effectively mobilize with plerixafor may be offered the option of bone marrow harvest for collection of back-up cells only, provided that drug product manufactured from mobilized cells has met criteria for dispositioning for clinical use.

As of Version 8.0 of this protocol, Group C will include adolescent subjects ≥ 12 and < 18 years of age in addition to subjects ≥ 18 and ≤ 50 years of age. It should also be noted that while all Group A subjects and some Group B subjects received drug product manufactured using “Process 1”, all current and future Group C subjects will receive drug product manufactured using an optimized process termed “Process 2”. Treatment with drug product manufactured using Process 2 (versus Process 1) has resulted in increased drug product VCN, peripheral blood VCN, and HbA^{T87Q} levels across multiple bluebird bio-sponsored clinical studies.

The drug product must be release tested and dispositioned for clinical use and stored at the study site before the subject can begin myeloablative conditioning with busulfan.

Stage 3 –Myeloablative conditioning and infusion of bb1111

The subject’s suitability for transplant will be reconfirmed with clinical laboratory tests (complete blood count [CBC], serum chemistry, liver function tests, and pregnancy test), physical examination, performance status, cytogenetics, and other tests based on institutional requirements. The results of these tests will be reviewed, and availability of the drug product on site and the availability of back-up cells will be confirmed before the site can proceed with conditioning.

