17. Any prior or current malignancy or immunodeficiency disorder, except previously treated, non-life threatening, cured tumors such as squamous cell carcinoma of the skin.
18. Prior receipt of an allogeneic transplant.

19. Immediate family member with a known or suspected Familial Cancer Syndrome (including but not limited to hereditary breast and ovarian cancer syndrome, hereditary non-polyposis colorectal cancer syndrome, and familial adenomatous polyposis).
20. Diagnosis of significant psychiatric disorder of the subject that, in the Investigator's judgment, could seriously impede the ability to participate in the study.
21. Pregnancy, or breastfeeding in a postpartum female, or absence of adequate contraception for fertile subjects. Females of childbearing potential must agree to use a medically acceptable method of birth control such as oral contraceptive, intrauterine device, barrier and spermicide, or contraceptive implant/injection from time of consent through at least 6 months after drug product infusion. Male subjects must agree to use effective contraception (including condoms) from Conditioning through at least 6 months after drug product infusion.
22. Participation in another clinical study with an investigational drug within 30 days of Screening.
23. Previous Exclusion Criterion #23 is no longer applicable as of Protocol Amendment 8.0.
24. Prior receipt of gene therapy.
25. Previous Exclusion Criterion #25 is no longer applicable as of Protocol Amendment 9.0.
26. An assessment by the Investigator that the subject or parents/caregivers (as required) will not be able to comply with the study procedures outlined in the study protocol.
27. Patients needing therapeutic anticoagulation treatment during the period of conditioning through platelet engraftment (patients on prophylactic doses of anticoagulants not excluded per this criteria).
28. Unable to receive RBC transfusion.
29. Any other condition that would render the subject ineligible for HSCT, as determined by the attending transplant physician.
30. Applicable to subjects < 18 years of age only: Availability of a willing, matched HLA-identical sibling hematopoietic cell donor.

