5.2.5. Conditioning

5.2.5.1. Busulfan Dosing

Myeloablative conditioning of the subject will be performed using busulfan. Conditioning will only begin after the following criteria are met:

- all drug product lots to be used for the subject have been release tested, dispositioned for clinical use, and stored at the clinical site
- a sufficient number of back-up cells has been collected and stored at the clinical site
- the subject has undergone interim assessments for updated medical history, AE, concomitant medications, physical examination, vital signs, and laboratory tests, all as per the SOE, and continues to meet the eligibility criteria based on these results
- subjects have undergone a transfusion regimen ($Hb > 10 \text{ g/dL}$ and $HbS < 30\%$) and are off HU for at least 2 days and iron chelation for at least 7 days prior to the start of conditioning
- results of conventional cytogenetics (karyotyping) and cytogenetics by FISH from the bone marrow have been received and reviewed by the Investigator and the Medical Monitor; in the presence of a chromosomal abnormality or genetic mutation that does not render the subject ineligible for HSCT per the Investigator's judgment, approval of the Medical Monitor is required before the subject can proceed with conditioning

(see [Section 6.2.11](#)) and subject must sign appropriate informed consent before proceeding with conditioning and treatment with bb1111.

Busulfan will be administered at a starting dose of 3.2 mg/kg/day for 4 consecutive days via IV infusion on Days -6 through -3. The preferred schedule is busulfan via a central venous line (CVL) as a 3-hour infusion once daily for 4 consecutive days for a total of 4 doses. Divided dosing is permitted. In this case, busulfan should be administered as a 2-hour infusion every 6 hours for 16 consecutive doses. For subjects weighing < 35 kg, a q6h dose of 0.8 mg/kg is preferred; for subjects weighing \geq 35 kg, either once daily (qd) or q6h dosing can be used, at the discretion of the Investigator. Please note that the timing of busulfan PK sample collection is based on whether a 2-hour or 3-hour infusion is used.

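### The pre-busulfan results check covers karyotype and FISH but not the scheduled NGS test, although a mutation found before conditioning triggers Medical Monitor approval and consent

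*Protocol*

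**What the plan says.** Protocol 5.2.5.1 lists what must be true before conditioning. One bullet requires that "results of conventional cytogenetics (karyotyping) and cytogenetics by FISH from the bone marrow have been received and reviewed" by the Investigator and the Medical Monitor. The same bullet then says that, "in the presence of a chromosomal abnormality or genetic mutation that does not render the subject ineligible for HSCT", the Medical Monitor must approve and the subject must give appropriate informed consent before going on. Section 8.3 repeats the consent duty for a concerning mutation found before conditioning.

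A separate bullet in 5.2.5.1 asks for interim assessments that include "laboratory tests, all as per the SOE, and continues to meet the eligibility criteria based on these results".

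Table 3 has a row for central-laboratory blood NGS in the Preconditioning column. Footnote q lets that sample be taken at any time before conditioning and says nothing about when the result is due. Table 3 has a row for bone marrow karyotyping but none for FISH.

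The other places that describe the suitability check are:

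- Section 3.1, Stage 3, relies on "clinical laboratory tests (complete blood count [CBC], serum chemistry, liver function tests, and pregnancy test), physical examination, performance status, cytogenetics" and tests required by the institution.
- Table 3 footnote t and section 6.2.11 list cytogenetics among the items reviewed.
- Section 6.2.18 names karyotyping and NGS as the assays, then states: "Results from conventional cytogenetics (karyotyping) from the bone marrow prior to conditioning will be used to assess suitability for transplant".

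**The concern.** In 5.2.5.1 the list of results that must be read is narrower than the list of findings that require action. The action rule covers chromosomal abnormalities and genetic mutations. The results rule covers karyotype and FISH. The one test that the schedule labels as mutational, blood NGS, is outside it.

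Busulfan myeloablation cannot be undone. Medical Monitor approval and informed consent about a mutation protect the subject only if the mutation is known before the first dose. If the NGS result arrives afterwards, both steps come too late. Section 6.2.18 directs this testing particularly at changes associated with MDS and AML, and mutations associated with hematologic malignancy are a safety endpoint in 2.2.3.

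**Working it through.** No sample size, power or error rate enters this point, so the check is a comparison of texts followed by a short count.

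**1. Which results must be read, and which findings require action?**

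| Place in Protocol | Result to be read or used | Finding that triggers action |
|---|---|---|
| 5.2.5.1 | Karyotype and FISH | Chromosomal abnormality or genetic mutation: approval and consent |
| 8.3 | None named | Chromosomal abnormality or genetic mutation: consent |
| 6.2.11 | Cytogenetics; marrow assessed by karyotyping | Chromosomal abnormality only: withdrawal, or approval and consent |
| 6.2.18 | Karyotype | None stated |
| 3.1 Stage 3; Table 3 footnote t | Cytogenetics | None stated |

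NGS does not appear in the middle column. A mutation appears in the right-hand column in 5.2.5.1 and 8.3, but not in 6.2.11, so 6.2.11 and 5.2.5.1 do not match.

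**2. Does the timing rule close the gap?** Footnote q governs collection only. A sample drawn just before busulfan complies, whether or not its result is back.

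**3. Does the general laboratory bullet in 5.2.5.1 close it?** It does not name NGS. Where the protocol itemises such tests, NGS is absent: 3.1 lists blood count, chemistry, liver function and pregnancy tests, and 6.2.7 covers "Blood samples for clinical laboratory tests, including hematology, serum chemistry, liver function tests, renal function tests, coagulation studies, and iron studies". The bullet also works through the eligibility criteria, and none of these names a mutation. The nearest is exclusion 29, a discretionary catch-all: "Any other condition that would render the subject ineligible for HSCT, as determined by the attending transplant physician".

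**4. Does 6.2.11 close it?** It says that "Bone marrow aspirate will be collected prior to conditioning for assessment of chromosomal abnormalities or genetic mutations", but it assigns that assessment to karyotyping. Section 6.2.18 lists NGS separately as the mutational test. The approval and consent rule in 6.2.11 then speaks of chromosomal abnormalities alone.

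**5. How many subjects could be affected?**

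- Planned in Group C: about 41 (Protocol 4.1).
- Infused in Group C: 36 (SAP 1.2.1, Table 1).
- Share infused: 36 / 41 = 87.8%.
- Remaining: 41 − 36 = about 5, and 5 / 41 = 12.2%.

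The range is 0 to about 5. Zero is better supported: SAP 5.2 refers to an interim clinical study report already produced, sets analyses for the final one, and adds an engraftment analysis to agree with the product label.

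**The case against.** The best case against rests on four arguments.

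- **The general bullet may already include NGS.** It speaks of laboratory tests per the schedule without the word clinical, whereas the itemised lists in 3.1 and 6.2.7 describe clinical laboratory tests. NGS is a scheduled blood test at that visit, so an investigator could reasonably take it as covered. That reading is possible. But the bullet neither names NGS nor plainly requires its result, and it leads back to eligibility criteria that are silent on mutations. If it already demanded every scheduled result, the separate cytogenetics bullet would be largely redundant.
- **Using karyotype alone may be deliberate.** Section 6.2.29 calls NGS supportive, and the pre-infusion sample serves as a baseline for the summaries before and after Day 1 in SAP 4.6.10. The mutation rule may only say what to do if a mutation happens to be known. The baseline role is real. It does not explain why approval and consent before an irreversible step depend on a mutation while the scheduled test for one need not be read. Section 6.2.29 also calls karyotyping supportive, and that result is required.
- **The mismatch may be editorial.** FISH is named in the results rule but not scheduled in Table 3, which suggests wording that was never harmonised. That may be how it arose, but the text sites follow is the same.
- **The practical reach is small and the evidence incomplete.** This stands. Probably no subject remains to be conditioned, no NGS turnaround time is given, and the Study Operations Manual or Laboratory Manual, neither of which was available, may set a deadline for the result.

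**Conclusion.** The concern holds as a point about the text: a site can follow the protocol and start busulfan with the NGS result unread, while approval and consent duties depend on what that result shows. The documents do not show that this happened. They do not say whether NGS was read before busulfan in the 36 infused Group C subjects.

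The size is low: 0 to about 5 future subjects, with 0 more likely. This rests on two assumptions: that the planned 41 still stands, since neither document states that accrual has closed, and that no operational manual already requires the result before conditioning. If either dosing is complete or a manual sets the timing, the sponsor can settle the point by saying so. It is worth considering and does not bear on the efficacy analysis.

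**What to change.** 1. In 5.2.5.1, add the pre-conditioning NGS result to those the Investigator and Medical Monitor must receive and review before busulfan.
2. In Table 3 footnote t, 6.2.11 and 6.2.18, refer to cytogenetics and NGS together.
3. In 6.2.11, extend the existing approval and consent rule to genetic mutations so that it matches 5.2.5.1. Leave withdrawal for a mutation to the Investigator's judgment and add no mandatory exclusion.
4. In footnote q, require the NGS draw early enough for the result to return before busulfan.

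The change is to protocol wording. The sample is already scheduled and may already be drawn early, and Protocol 5.5 expects about 2 months between mobilization and infusion. The cost is a possible delay to conditioning, of unknown length, during which the transfusion regimen continues. A long delay could also mean repeating pulmonary function tests once they are more than 3 months old. The Medical Monitor would have to review variants of uncertain significance.
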